**Table 1. Study and research visits**

Study arm	Assessment period (month)											
	0	1	2	3	4	5	6	7	8	9	10	11
Early 1												
Clinic visits	x			x			x					x
Pharmacy pick-up	x	x	x	x	x	x	x		x			x
Viral load						x						x
Early 2												
Clinic visits	x			x			x					x
Pharmacy pick-up	x	x	x	x	x	x	x		x			x
Viral load				x		x						x
Usual care												
Clinic visits	x			x			x		x			x
Pharmacy pick-up	x	x	x	x	x	x	x	x	x	x	x	x
Viral load					x							x
Research visits												
All arms		x				x						x

Data sources and collection:

- **Questionnaires/Surveys:** questionnaires will be administered to participants at each research visit (enrollment, 6 months, 12 months) using RedCap technology. We will collect data on demographics, HIV risk and diagnosis, medication adherence, quality of life, patient satisfaction, and anticipated or experienced HIV-related stigma.
- **Medical records:** we will extract data from participants' medical records, including HIV diagnosis date, ART initiation date, appointment and pharmacy visit dates, and medication regimen.
- **Laboratory/blood testing:** all participants will undergo lab testing including creatinine, CD4 count, liver function testing at study enrollment. Participants will undergo viral load testing at intervals noted above and at the study conclusion at 12 months. Tests will be processed at Rwanda Military Hospital's lab and results will be inputted into study databases and clinical registers.

**Table 2. Data collection**

Measure	Instrument/source	Research visit		
		Baseline	6 mo	12 mo
REDCAP Questionnaire				
Socio-demographic information	Sociodemographic form	x		
Quality of life	EQ-5D 	x	x	x
Patient satisfaction with care	Patient satisfaction with care 	x	x	x
Other healthcare utilization	Other healthcare utilization form	x	x	x
Medication adherence	7-day medication adherence recall		x	x
HIV stigma - anticipated	Earnshaw & Chadoor 	x	x	x
HIV stigma - experienced	HASI-P 	x	x	x
Patient costs/expenditures	Patient expenditure form	x	x	x
Medical record				
Enrollment data (date of diagnosis, date of enrollment, date of ART)		x		
Appointment adherence		x	x	x
Pharmacy visit adherence		x	x	x
ART regimen		x	x	x
Laboratory				
Baseline laboratory test (creatinine, CD4, liver)		x		
Viral load		Per protocol above		

### Data management

Data collected during from patient questionnaires during study visits will be entered directly by study staff into the RedCap database using the participant's study ID. Data from the medical records (paper charts) will be regularly extracted and entered into the RedCap study database using the participant's study ID. Laboratory test results will be obtained from the Rwanda Military Hospital lab and will be entered into the RedCap study database using the participant's study ID. Results will also be provided to the participants' health center.

The RedCap database will be housed on an encrypted, password-protected computer at Rwanda Military Hospital. Only project staff will have access to this database. All patient identifiers will be scrubbed from the database and participants will only be referenced by a study ID. A crosslink from study ID to patient identifiers will only be available to study personnel in a separate password-protected folder stored on a different encrypted computer at Rwanda Military Hospital. Participant's consent forms will be stored separately from research data in locked file cabinets on site at Rwanda Military Hospital.

### Main outcome variables

- **Preliminary efficacy:** *Primary outcome* is viral suppression (defined as viral load <200) at 12 months (yes/no). *Secondary outcome* is appointment and pharmacy adherence (attended all appointments/missed ≥1 appointment).
- **Feasibility/acceptability:** patient satisfaction with appointment schedule, health worker satisfaction with appointment schedule, patient experiences of stigma
- **Cost:** we will collect data on patient-level costs borne by patient or relatives of the patient towards their care (i.e. transportation to clinic, missed days of work). To ascertain the cost to the health facility, we will estimate fixed (i.e. equipment, human resources) and variable (i.e. type and number of visits, laboratory tests, inpatient care) costs to care.

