The objectives of this study are to thus pilot test the effect of reducing time to spaced-out appointments from 18 to 6 months for newly-diagnosed PLWH in Rwanda. This is a critical time to conduct this work, as most African countries have adopted differentiated care models. Rwanda, where this study is based, was among the first countries to implement Treat All as a national policy and remains a leader in HIV outcomes. To better understand the effects of early spaced-out appointments as well as the degree of viral load monitoring needed to determine stability, we will conduct a 3-arm pilot intervention study. We will enroll 90 patients: 30 will be randomized to 6-month advancement to spaced out appointments after 1 suppressed viral load (at 5 months after enrollment) (“*Early 1*”); 30 will be randomized to 6-month advancement to spaced-out appointments after 2 suppressed viral loads (at 3- and 5-months after enrollment) (“*Early 2*”); and 30 will be randomized to continue in usual care (“*Usual care*”). We will compare the study arms with respect to viral suppression at 12 months after enrollment (primary outcome) and appointment/ pharmacy adherence (secondary outcome). We hypothesize that reducing the time to the “clinically stable” phase to 6 months will be feasible, acceptable, not inferior to usual care with respect to viral suppression or adherence, and will be cost-effective. The specific aims of this study are:

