**Aim 1: measure the preliminary efficacy, feasibility and acceptability of early spaced-out appointments.**

- a. Preliminary efficacy: We will compare intervention arms to the usual care arm with respect to 12-month viral suppression (primary outcome) and appointment/pharmacy adherence (secondary outcomes). *Hypothesis: We hypothesize that outcomes will not be inferior in the intervention arms compared to the usual care arm.*
- b. Feasibility. We will examine process measures (patient enrollment, patient waiting time, staff effort) at the end of the trial.
- c. Acceptability. We will assess patient and care provider satisfaction at the end of the trial.

**Aim 2: measure the cost-effectiveness of early spaced-out appointments.** We will collect patient- and health center data on costs, including transportation, specimen testing, and potential cost of downstream outcomes. *Hypothesis: we hypothesize that short-term cost will be higher in the “Early 2” arm compared to “Early 1” and “Usual care,” but that long-term costs will be lower in the “Early 1” and “Early 2” arms compared to the “Usual care” arm.*

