### Clinical visits: Intervention and usual care arms

- **Early spaced-out appointments after 1 suppressed viral load – Early 1.** Patients enrolled in this arm will pick up medications monthly at the pharmacy and attend clinical appointments every 3 months until 6 months after entering HIV care. They will have a viral load measured at month #5 after entering HIV care. If their viral load is suppressed, they will advance to spaced out appointments at month #6 after entering HIV care, picking up medications every 3 months and attending clinical appointments every 6 months.
- **Early spaced-out appointments after 2 suppressed viral loads – Early 2.** Patients enrolled in this arm will pick up medications monthly at the pharmacy and attend clinical appointments every 3 months until 6 months after entering HIV care. They will have a viral load measured at month #3 and #5 after entering HIV care. If both viral loads are suppressed, they will advance to spaced out appointments at month #6 after entering HIV care, picking up medications every 3 months and attending clinical appointments every 6 months.
- **Standard of care – Usual care.** Patients enrolled in this arm will pick up medications monthly at the pharmacy and attending clinical appointments every 3 months for the duration of the study. They will have a viral load measured at month #5 after entering HIV care.

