### Data analysis

- **Assessment of randomization:** we will compare all covariates between the 3 study arms, using t-tests (or non-parametric tests) for continuous variables and chi-square (or Fisher tests) for categorical variables.
- **Preliminary efficacy:** We hypothesize that viral suppression and appointment/pharmacy adherence will be similar across the 3 study arms. We will first compare proportions of patients achieving viral suppression and attending all appointment/pharmacy visits using chi-square tests. We will use generalized estimating equations to estimate risk differences, risk ratios and associated 95% confidence interval for the effect of each intervention arm compared to the control. The non-inferiority limit will be set at 10%. Because of the small number of participants we will be able to enroll in this pilot study, it may not be sufficiently powered to detect a statistically significant differences in outcomes. However, the findings and the effect size obtained from this study will provide key results on intervention feasibility and guide a future, larger study to test intervention efficacy.
- **Cost analysis:** We hypothesize that the intervention arms will result in reduced patient-level and health-center costs. Outcomes will include: (a) annual cost per patient in each cohort/arm (per patient year cost); and (b) cost-effectiveness of the intervention arms compared with usual care.

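### The all-or-none adherence outcome favours the early arms at equal per-visit attendance, because participants who advance have fewer visits to miss after month 6

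*Combined protocol and SAP*

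**What the plan says.** Under Main outcome variables, the secondary efficacy outcome is "appointment and pharmacy adherence (attended all appointments/missed ≥1 appointment"). Under Data analysis, the arms are first compared on the proportion "attending all appointment/pharmacy visits using chi-square tests", and then by risk differences and risk ratios for each early arm against usual care. The same paragraph states "The non-inferiority limit will be set at 10" per cent and does not confine that limit to viral suppression. Section B hypothesises that early advancement is "not inferior to usual care with respect to viral suppression or adherence", and Aim 1a repeats that "outcomes will not be inferior in the intervention arms compared to the usual care arm".

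Under Clinical visits, all arms share one schedule to month 6. Early-arm participants who meet the viral load condition then change to "picking up medications every 3 months and attending clinical appointments every 6 months". Usual-care participants "pick up medications monthly at the pharmacy and attending clinical appointments every 3 months for the duration of the study".

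Nothing in the plan adjusts the adherence outcome for the number of visits scheduled, sets a common counting window, or says how late a visit must be to count as missed. The schedule after month 6 for early-arm participants who do not advance is not stated.

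**The concern.** Attending every visit is harder when there are more visits. The intervention reduces the number of visits, so the outcome's denominator differs by arm. Two arms whose patients attend equally reliably will then show different proportions, with the early arms ahead.

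That direction matters because the hypothesis is non-inferiority. A shift in favour of the early arms can offset a real fall in attendance after spacing, which is the harm that the comparison should be able to show. The bias is systematic, so a larger trial using the same definition would estimate it more precisely without removing it. The plan says that the findings and effect size will "guide a future, larger study to test intervention efficacy".

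**Working it through.** The plan gives no adherence figure to reproduce. Every attendance, correlation and advancement rate below is an assumption.

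**Visit counts, from Clinical visits.** Month 0 is left out because participants are already in care and on ART when they enrol.

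| | Months 1–6, all arms | After month 6, advanced | After month 6, usual care | Months 1–12, advanced v usual care |
|---|---|---|---|---|
| Pick-ups | 6 | 2 (months 9, 12) | 6 (months 7–12) | 8 v 12 |
| Clinic visits | 2 (months 3, 6) | 1 (month 12) | 2 (months 9, 12) | 3 v 4 |

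**Direction.** The advanced schedule is a subset of the usual-care schedule. If attendance behaviour is the same, the chance of no miss cannot be lower on the subset, whatever the within-person correlation.

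**Size.** With per-visit attendance q and k visits, P(all attended) = q^k for independent visits. With within-person correlation (ICC) ρ, a beta-binomial gives P = ∏(a+i)/(s+i) for i = 0 to k−1, where s = (1−ρ)/ρ and a = qs. All early-arm participants are taken to advance.

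| q | Pick-ups, independent | Pick-ups, ICC 0.3 | Clinic, independent | Clinic, ICC 0.3 |
|---|---|---|---|---|
| 95% | 66.3 − 54.0 = +12.3 | +3.2 | +4.3 | +2.0 |
| 98% | 85.1 − 78.5 = +6.6 | +1.5 | +1.9 | +0.8 |
| 99% | 92.3 − 88.6 = +3.6 | +0.8 | +1.0 | +0.4 |

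Table 1 is broken in the text available, so the counts rest on the prose. Using its printed pharmacy marks instead (9 v 12) gives 63.0 − 54.0 = +9.0 at 95% with independent visits.

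**Partial advancement.** Suppose 80% advance and non-advancers keep the usual-care schedule. At 95%, the independent-visit shift is 0.8 × 12.3 = +9.8. If advancers attend 97% and non-advancers 87%, it is 0.8 × (0.97^8 − 0.97^12) = +7.2. Early 2 requires two suppressed viral loads and Early 1 only one, so the shift may be smaller in Early 2.

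**Fall that would show as zero difference (pick-ups).** With independent visits, early-arm attendance x after month 6 satisfies x² = q^6, so x = q³: 85.7%, 94.1% and 97.0% when usual care is at 95%, 98% and 99%. With ICC 0.3, x = q√(P12/P8): 93.1%, 97.2% and 98.6%.

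**Against the 10% limit.** This is exact enumeration of two binomials with 30 per arm, giving the probability that the lower two-sided 95% limit exceeds −10 points. "Without" sets both arms to the usual-care probability.

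| Scenario | Wald, with v without shift | Newcombe, with v without shift |
|---|---|---|
| 95%, independent | 43% v 12% | 43% v 12% |
| 95%, ICC 0.3 | 27% v 17% | 23% v 15% |
| 98%, ICC 0.3 | 42% v 32% | 26% v 19% |

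**Precision of the replacement measure.** For the participant-level proportion attended after month 6, the 95% half-width is 1.96 × √((v_e + v_u)/30), with v = q(1−q)(1+(k−1)ρ)/k. Over ICC 0 to 0.3 it is 6.4–8.1 points for pick-ups and 9.6–10.0 for clinic visits at 95% attendance, and 4.1–5.2 and 6.1–6.4 at 98%.

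**The case against.** The strongest reply is that fewer visits to miss is what the intervention is meant to achieve. Attending everything that was scheduled is then a legitimate measure of how manageable each schedule is. That stands, and it is a reason to keep the figure. It does not support reading the figure as non-inferior adherence.

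Second, repeated visits by one person are unlikely to be independent, and the large figures need independence. With ICC 0.3 the pick-up shift is 0.8 to 3.2 points. The 95% half-width of the all-or-none difference is then about 20, 14 and 10 points at 95%, 98% and 99% attendance, so the shift would be small beside sampling error. This also stands. The documents support neither correlation, so only the direction is firm.

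Third, Data analysis also predicts that adherence will be similar across arms, and a shift favouring the early arms moves away from similarity. The concern therefore bites on the non-inferiority wording in Section B and Aim 1a. The 10% limit is not tied to a named outcome, so applying it to adherence is an inference, though the risk difference is biased with or without a limit.

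Finally, this is a secondary outcome in a 90-person pilot that admits low power, and 12-month viral suppression is untouched. That limits the weight of the point without removing it.

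**Conclusion.** The concern holds. At equal per-visit attendance, the planned adherence comparison favours the early arms through participants who advance, and the plan does not correct for it. The direction follows from the schedules, provided that non-advancers keep the usual-care schedule. The documents do not state that schedule, and they plan adherence intensification for unsuppressed patients in any arm.

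The size cannot be fixed from the documents. With full advancement and 95–99% attendance, the pick-up shift runs from under 1 point (99%, ICC 0.3) to about 12 points (95%, independent visits), and the clinic shift from 0.4 to 4.3 points. Partial advancement reduces both. At the upper end the shift alone exceeds the 10-point limit; at the lower end it is negligible beside the interval width. This should be fixed because adherence is the only secondary efficacy outcome named, the bias runs in the unsafe direction for non-inferiority, and the correction is cheap.

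**What to change.** **Outcome.** Replace the all-or-none comparison with each participant's proportion of scheduled visits attended, for clinic and pharmacy separately, with one lateness rule for all arms. Make the main comparison the period after month 6 to month 12, by randomised arm, with non-advancers included on their own scheduled count. State, identically for all arms, how participants lost, transferred or deceased are counted.

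**Analysis.** Use one record per participant, equally weighted, with a small-sample-corrected robust variance; uncorrected intervals covered 86–97% in simulation. Do not weight by visits. With 80% advancing and attendance of 97% (would advance) and 87% (would not) in both arms, visit weighting puts the early arm at (0.8×2×0.97 + 0.2×6×0.87)/(0.8×2 + 0.2×6) = 92.7% against 95.0%, a spurious −2.3 points. Equal weighting gives zero.

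**Whole-year figure, if wanted.** Compute months 1–6 and 7–12 separately and combine them with the same weights in every arm. A plain annual pick-up ratio gives months 1–6 a weight of 6/8 in advanced participants and 6/12 in usual care. An identical fall from 97% to 93% then appears as +1.0 point, and a real 10-point early-arm fall after month 6 appears as only −2.5.

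**Supporting measures.**
- Count the same months in every arm (pick-ups 1–6, 9 and 12; clinic 3, 6 and 12). This gives 8 v 8 and 3 v 3, so there is no artefact at equal attendance. It discards usual-care pick-ups in months 7, 8, 10 and 11.
- A missed pick-up covers one month in usual care and three after advancement. Report the proportion of days covered as well, if days supplied can be derived.
- Keep "attended all" as a descriptive visit-burden measure without the 10% limit. Justify a limit for the new scale, or report the difference with its 95% interval.

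**Cost.** A revised outcome definition and a short analysis paragraph. Visit dates are already extracted, and Table 2 lists appointment and pharmacy adherence separately. Advancement status must be derived from viral loads and the chart, and days supplied is not on the extraction list. Advanced participants contribute only 2 pick-ups and 1 clinic visit after month 6, hence the half-widths shown above. A small residual remains: early pick-ups fall on average at month 10.5 and usual-care pick-ups at 9.5, so a decline of 1 point per month shifts the difference by −1.0 point. The matched-months count avoids this.

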### Data analysis

- **Assessment of randomization:** we will compare all covariates between the 3 study arms, using t-tests (or non-parametric tests) for continuous variables and chi-square (or Fisher tests) for categorical variables.
- **Preliminary efficacy:** We hypothesize that viral suppression and appointment/pharmacy adherence will be similar across the 3 study arms. We will first compare proportions of patients achieving viral suppression and attending all appointment/pharmacy visits using chi-square tests. We will use generalized estimating equations to estimate risk differences, risk ratios and associated 95% confidence interval for the effect of each intervention arm compared to the control. The non-inferiority limit will be set at 10%. Because of the small number of participants we will be able to enroll in this pilot study, it may not be sufficiently powered to detect a statistically significant differences in outcomes. However, the findings and the effect size obtained from this study will provide key results on intervention feasibility and guide a future, larger study to test intervention efficacy.
- **Cost analysis:** We hypothesize that the intervention arms will result in reduced patient-level and health-center costs. Outcomes will include: (a) annual cost per patient in each cohort/arm (per patient year cost); and (b) cost-effectiveness of the intervention arms compared with usual care.

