### Study participants, recruitment and enrollment

- **Inclusion/exclusion criteria:** *Inclusion* criteria for the study are: 1)  $\geq 15$  years; 2) newly-diagnosed with HIV; 3) enrolled in care at study health facility; 4) initiated ART. *Exclusion criteria* are: 1) planning on moving away from health center/Kigali in the next 12 months; 2) unable to provide informed consent; 3) enrolled in care while pregnant; 4) co-infected with tuberculosis; 5) concurrent known mental health or substance use disorder.
- **Recruitment:** A study research assistant will work with staff at the health facility to identify persons who are newly-diagnosed with HIV and may be eligible for the study. We will have clinic nurses inform potentially eligible patients about the study during appointments and provide study contact information. We will also put up posters in health facilities with study information.
- **Screening procedures:** The research assistant will meet with interested participants to describe the study and offer enrollment during a follow-up appointment after their enrollment into care. Patients who are interested in participating in the study, who meet criteria and who provide written informed consent will be enrolled in the study and be randomized to either the intervention arms or the standard of care arm.
- **Randomization:** randomization will be stratified by age ( $<24$  vs  $\geq 24$ ) and by clinic and occur in blocks of 4-8, with 1:1:1 allocation of the three study arms.

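### Baseline significance tests cannot assess randomisation (and a t-test does not fit three arms), while the efficacy analysis names neither stratification factor, so its interval tends to be somewhat too wide

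*Combined protocol and SAP*

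**What the plan says.** The Data analysis section opens with an item on assessing randomisation: "we will compare all covariates between the 3 study arms, using t-tests (or non-parametric tests) for continuous variables". For the remaining covariates it names "chi-square (or Fisher tests) for categorical variables". It gives no list of covariates, no significance level, no pairing rule and no consequence of a significant result.

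Under Study participants, recruitment and enrollment, "randomization will be stratified by age" (under 24 against 24 and over) "and by clinic and occur in blocks of 4-8". The ratio is given there as "with 1:1:1 allocation of the three study arms". Section B sets the size: "We will enroll 90 patients: 30 will be randomized to 6-month advancement to spaced out appointments after 1 suppressed viral load", with 30 in each of the other two arms.

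For efficacy, Data analysis plans chi-square tests of the proportions. Generalized estimating equations (GEE) then give risk differences, risk ratios and 95% confidence intervals "for the effect of each intervention arm compared to the control". The non-inferiority limit is 10%. No covariate, stratum, cluster unit or link function is named for this model, and no other section adds one.

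**The concern.** There are two separate matters.

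**Baseline tests.** A t-test takes two groups. For three arms it must either be run pairwise or be replaced by a three-group test. More basically, when allocation was truly random, the null hypothesis of a baseline test is already known to be true. A small p-value then reflects chance, and a large one with 30 per arm does not show balance. Presented as an assessment of randomisation, the tests may cast doubt on a sound allocation, and the plan leaves open how the team would respond.

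**Efficacy analysis.** Stratified randomisation balances the arms on age group and clinic. If either factor predicts suppression, that balance reduces the true variability of the difference between arms. A standard error that ignores the strata does not credit the reduction. The protocol itself treats age as prognostic: the rationale for the inclusion criteria (section D) and section E say that patients aged 15–24 are at particular risk of poor outcomes. At stake is the width of the interval that is set against the 10% limit.

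**Working it through.** The plan gives no figure of its own on this point, so there is nothing to reproduce first.

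**Inputs from the protocol:** three arms of 30; strata of age (2 levels) by clinic. Study setting names four sites, giving up to 4 × 2 = 8 strata, although it also speaks of three facilities. Table 2 marks 12 rows at baseline. Some are single instruments, some hold several variables ("Baseline laboratory test (creatinine, CD4, liver" is one row), and some are categorical.

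**Assumptions:** two-sided 0.05; 5 to 20 independent covariates; 30% of patients under 24; the suppression rates in the table below.

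**1. False flags per continuous covariate.** Simulation of 40,000 trials with correct randomisation, 30 per arm and a normal covariate:
- one-way analysis of variance: 4.9%
- t-tests of each early arm against usual care: 9.0% with at least one p < 0.05
- t-tests of all three pairs: 12.2%

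**2. False flags across k covariates, one valid three-group test each.** P(at least one) = 1 − 0.95^k:
- k = 5: 23%
- k = 8: 34%
- k = 10: 40%
- k = 15: 54%
- k = 20: 64%

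Correlation between covariates lowers these figures.

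**3. Standard error of the risk difference, ignoring or using the age stratum.** Two arms of 30, each with exactly 9 younger and 21 older patients, and the same rates in both arms. Let p_y and p_o be suppression in younger and older patients, and p = 0.3p_y + 0.7p_o.

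- Unadjusted SE = √[2p(1 − p)/30]
- Stratified SE = √{2[9p_y(1 − p_y) + 21p_o(1 − p_o)]/30²}

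For p_y = 0.75 and p_o = 0.95, p = 0.89. The unadjusted SE is √(2 × 0.89 × 0.11/30) = 0.0808. The stratified SE is √[2(1.6875 + 0.9975)/900] = 0.0772. The ratio is 1.05.

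| Younger / older | Unadjusted SE | Stratified SE | Ratio | Coverage of unadjusted 95% CI (20,000 simulations) |
|---|---|---|---|---|
| 85% / 92% | 0.0778 | 0.0774 | 1.01 | 94.4% |
| 75% / 95% | 0.0808 | 0.0772 | 1.05 | 95.4% |
| 65% / 97% | 0.0857 | 0.0769 | 1.11 | 96.6% |
| 50% / 98% | 0.0956 | 0.0769 | 1.24 | 97.8% |

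**4. The same with realistic, imperfect balance.** Simulated trials of 90 patients, four equal clinics, 30% younger, blocks of 6 (the only size from 4 to 8 divisible by three) and no clinic effect, all assumed. Over the same four scenarios the unadjusted SE exceeds the true standard deviation by about 1% in the first and about 17–18% in the last. A Mantel-Haenszel risk difference with its stratified variance has an SE within about 3% of the true standard deviation throughout.

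**5. Against the limit.** Taking the 10% as an absolute risk difference (the scale is not stated), the 95% half-width in the second scenario is 1.96 × 0.0808 = 15.8 points unadjusted and 1.96 × 0.0772 = 15.1 points stratified. In the last it is 1.96 × 0.0956 = 18.7 against 1.96 × 0.0769 = 15.1.

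**The case against.** The strongest reply is that this is a pilot that admits it may be underpowered, that t-tests may be loose wording for a routine baseline table, and that nothing in the plan hangs on those tests. Chi-square and Fisher tests handle three arms, and the unnamed non-parametric test may do so too. Much of this stands: the misfit is confined to the t-test.

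Several stronger readings are tempting, but the documents do not support them.
- A reader might infer that a sound randomisation will probably be reported as imbalanced. Pairwise t-tests on ten covariates would give 1 − (1 − 0.122)^10 = 73%. The plan does not say that every covariate is tested pairwise, and several are categorical. With one valid test each, ten covariates give 40%.
- A reader might infer that baseline p-values will select covariates for the efficacy model. The plan links no action to them, and the protocol identifies age as important on other grounds.
- A reader might take the factors to be deliberately excluded. They are only unnamed. GEE clustered by clinic is a possible reading, though with at most four clinics its robust variance would be unreliable.
- A reader might put a number on failures per arm. The documents give no expected suppression rate for this trial.

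On precision, the reply is also partly right. With weakly prognostic age the interval is essentially correct already (94.4% coverage), and stratifying changes the estimator's true variability little. What it chiefly corrects is the size of the reported standard error.

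**Conclusion.** The point holds in a limited form. The baseline tests cannot do what their label says, and the t-test named for continuous covariates is a two-group test. The chance of at least one false flag is about 23% to 64% for 5 to 20 independent covariates at 0.05 with valid three-group tests. Pairwise t-tests raise the rate per continuous covariate from about 5% to about 12%.

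Not naming age group and clinic in the efficacy analysis causes no bias in the risk difference. It leaves the standard error about 1% too large if age is weakly prognostic and up to about 18–24% too large if it is strongly so. The suppression rates and the 30% share of younger patients behind those figures are assumptions. The direction is unhelpful to a non-inferiority claim, but even the stratified half-width is about 15 points against a limit of 10. Sample size is the main constraint, and this is a modest improvement in the analysis.

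**What to change.** 1. Estimate the risk difference and risk ratio for each early arm against usual care by Mantel-Haenszel, stratified by age group and clinic, with the stratified variance. This tolerates zero cells. Report the unadjusted result alongside.
2. Replace the baseline tests with a descriptive table by arm (mean and SD, or number and percentage) without p-values. State that no covariate enters the efficacy model because of a baseline p-value.

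The cost is analysis wording only, since both factors are needed to randomise each patient. The downside is sparseness: 90 patients over up to 8 strata and three arms average 90/24 = 3.75 per cell. Strata with no patients in one of the two compared arms drop out of that comparison, and the number lost should be reported. An ordinary logistic model with these terms should be avoided, because with few failures it may separate.
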